3.2.13 Has a diagnosis of immunodeficiency (autoimmune disease) or is receiving chronic systemic steroid therapy (in dosing exceeding 10 mg daily of prednisone equivalent) or any other form of immunosuppressive therapy within 7 days prior to first dose of study treatment.

Note: Inhaled, intranasal, intraarticular, and topical corticosteroids and mineralocorticoids are allowed. Transient short-term use of systemic corticosteroids for allergic conditions (e.g., contrast allergy) is also allowed. Replacement therapy (e.g., thyroxine, insulin, or physiologic corticosteroid replacement therapy for adrenal or pituitary insufficiency, etc.) is not considered a form of systemic treatment and is allowed.

3.2.14 Has active autoimmune disease that has required systemic treatment in the past 2 years (i.e. with use of disease modifying agents, corticosteroids or immunosuppressive drugs). Replacement therapy (e.g., thyroxine, insulin, or physiologic corticosteroid replacement therapy for adrenal or pituitary insufficiency, etc.) is not considered a form of systemic treatment and is allowed.

3.2.15 Clinically significant cardiovascular disease, for example cerebrovascular accidents (less than 6 months, CVA) /stroke, myocardial infarction (also less than 6 months), unstable angina pectoris, New York Heart Association class 3 or 4 congestive heart failure, or serious cardiac arrhythmia requiring medication.

3.2.16 Uncontrolled hypertension defined as sustained blood pressure (BP) > 140 mm Hg systolic or > 90 mm Hg diastolic despite optimal antihypertensive treatment.

3.2.17 QT interval calculated by the Fridericia formula (QTcF) > 480 ms per electrocardiogram (ECG) within 14 days before first dose of study treatment.

Note: If a single ECG shows a QTcF with an absolute value > 500 ms, two additional ECGs at intervals of approximately 3 min must be performed within 30 min after the initial ECG, and the average of these three consecutive results for QTcF will be used to determine eligibility (i.e., if the average is ≤ 500 ms the patient is eligible).

3.2.18 Concomitant anticoagulation with or plan to use oral anticoagulants (warfarin, direct thrombin and Factor Xa inhibitors) or platelet inhibitors (e.g., clopidogrel). Allowed anticoagulants are the following:

- Prophylactic use of low-dose aspirin for cardio-protection (per local applicable guidelines) and low-dose low molecular weight heparins (LMWH).

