7.2.2 Adverse Events from Cabozantinib monotherapy

Consult the package insert and investigator brochure for the most current and complete information.

The **most frequent AEs experienced** by $\geq 20\%$ of subjects treated with Cabozantinib in descending order of frequency were diarrhea, fatigue, nausea, decreased appetite, vomiting, weight decreased, PPE, constipation, hypertension, dysgeusia, dysphonia, and asthenia. For a full description of the safety profile of Cabozantinib, refer to the Cabozantinib Investigator's Brochure.

Other **medically important** but less frequent AEs including arterial thrombotic AEs (e.g., TIA, and MI) and venous thrombotic AEs (e.g., DVT and PE), severe hemorrhagic events, proteinuria, wound-healing complications, GI perforation, abscesses including intra-abdominal and pelvic abscess, GI and non-GI fistula formation, osteonecrosis, and Reversible Posterior Leukoencephalopathy Syndrome (RPLS).

Adverse events associated with **laboratory abnormalities** experienced by $\geq 5\%$ of subjects treated with Cabozantinib in descending order of frequency were anemia, AST increased, ALT increased,

hypothyroidism, hypokalemia, hypomagnesemia, thrombocytopenia, hypocalcemia, hypophosphatemia, lactate dehydrogenase (LDH) increased, lipase increased, neutropenia, hyponatremia, ALP increased, leukopenia, and hyperglycemia.

Adverse events may occur within the first few weeks in the course of treatment with Cabozantinib, as Cabozantinib is expected to reach steady state exposure at approximately 2 weeks following first dose. Events that generally have an **early onset** include hypocalcemia, hypokalemia, thrombocytopenia, hypertension, PPE, abdominal pain, mucosal inflammation, constipation, diarrhea, and vomiting. Adverse events should be managed with supportive care at the earliest signs of toxicity. Dose reductions and treatment interruptions should be considered. Dose reductions are recommended for events that, if persistent, could become serious or intolerable.

Cabozantinib should be discontinued for the following AEs:

visceral perforation or fistula formation, severe hemorrhage, serious arterial thromboembolic events, nephrotic syndrome, hypertensive emergency, persistent uncontrolled hypertension despite optimal medical management, and RPLS.

Gastrointestinal Disorders

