Tolerable Grade 1-2 (duration < 48 h)	
 • Continue with study treatment and consider GI recommendations • Initiate treatment with an antidiarrheal agent (e.g., loperamide 4 mg followed by 2 mg after each episode of diarrhea [maximum: 16 mg loperamide per day]) • Dietary modifications (e.g., small lactose-free meals, bananas and rice) • Intake of isotonic fluids (1-1.5 L/day) • Re-assess after 24 hours: 
 ○ Diarrhea resolving to baseline bowel habits: gradually add solid foods and discontinue or decrease antidiarrheal treatment after 12 h diarrhea-free interval ○ Diarrhea not resolving: Continue/resume antidiarrheal treatment
Intolerable Grade 2, Grade 2 > 48 h, or \geq Grade 3	
 • Interrupt study treatment • Ask subject to attend clinic • Rule out infection (e.g., stool sample for culture) 
 ○ Administer antibiotics as needed (e.g., if fever or Grade 3-4 neutropenia persists > 24 h) • Administer fluids (1-1.5 L/day orally or IV, as appropriate) for hydration or to correct electrolyte abnormalities • For Grade 3-4 or complicated lower grade diarrhea consider hospitalization and IV hydration • Re-assess after 24 h 
 ○ Diarrhea resolving to baseline bowel habits or Grade \leq 1: consider restarting study treatment at reduced dose ○ Diarrhea not resolving: Start and/or continue antidiarrheal treatment (e.g., loperamide 4 mg followed by 2 mg after each episode of diarrhea [maximum: 16 mg loperamide per day]). Consider starting second line antidiarrheal or referral to gastroenterologist

Table 15. Management of Hypertension Associated with Cabozantinib

Event	Management
Subjects NOT receiving optimized anti-hypertensive therapy	
> 140 mm Hg (systolic) ^a and < 160 mm Hg OR > 90 mm Hg (diastolic) and < 110 mm Hg	
 Optimize antihypertensive medications by adding new or additional antihypertensive medications and/or increase dose of existing medications. Reduce cabozantinib treatment by one dose level if optimal antihypertensive therapy (usually to include 3 agents) does not result in BP <140 mm Hg systolic or <90 mm Hg diastolic If subject is symptomatic interrupt cabozantinib treatment

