≥ 160 mm Hg (systolic) OR ≥ 110 mm Hg (diastolic)	
 Reduce cabozantinib by one dose level^b or interrupt cabozantinib treatment per Investigator discretion. Add new or additional anti-hypertensive medications and/or increase dose of existing medications and monitor subject closely for hypotension. If optimized antihypertensive therapy (usually to include 3 agents) does not result in BP < 140 mm Hg systolic or < 90 mm Hg diastolic, cabozantinib treatment should be dose reduced further or interrupted. Cabozantinib treatment should be dose interrupted if upper limits of systolic BP (≥ 160 mm Hg) are sustained and not adequately manageable or if systolic BP is > 180 mm Hg or diastolic BP > 110 mm Hg, or if subject is symptomatic. Re-start cabozantinib treatment at the most tolerable dose and re-escalate only if BP falls to and is sustained at < 140 mm Hg systolic and < 90 mm Hg diastolic.
Hypertensive emergency ^c	
 Discontinue cabozantinib treatment.

^a Permitted dose levels are defined by individual protocols.

^b Hypertensive emergency is defined as uncontrolled elevated BP with clinical evidence of progressive or impending end-organ damage (e.g., myocardial infarction/ischemia, intracranial hemorrhage, cerebral ischemia, pulmonary edema, encephalopathy, kidney damage).

Table 16. Management of Palmar-plantar Erythrodysesthesia (PPE) associated with Cabozantinib

CTCAE v.4.0 Grade	Action To Be Taken
Grade 1	Cabozantinib treatment may be continued at the current dose if PPE is clinically insignificant and tolerable. Otherwise, Cabozantinib should be reduced to the next lower dose level ^a . Start urea 20% cream twice daily AND clobetasol 0.05% cream once daily. Reassess at least weekly; if PPE worsens at any time or does not improve after 2 weeks, proceed to the intervention guidelines for Grade 2.
Grade 2	Cabozantinib treatment may be continued if PPE is tolerated. Cabozantinib should be dose reduced or interrupted if PPE is intolerable. Continue urea 20% cream twice daily AND high potency steroid cream (e.g., clobetasol 0.05%) once daily and add analgesics (e.g., NSAIDs/gamma-aminobutyric acid agonists) for pain control if needed. Reassess at least weekly; if PPE worsens or affects self-care, proceed to the intervention guidelines for Grade 3.

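### Two dose-reduction bullets in the hypertension table (Appendix E, Table 15) say *or* where *and* is needed, so read literally they do not act when only one blood pressure target is missed

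*Combined protocol and SAP*

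**What the plan says.** Table 15 has two pressure rows, each entered on either component. Row 1 takes systolic above 140 "and < 160 mm Hg OR > 90 mm Hg (diastolic) and < 110 mm Hg". Row 2 takes systolic of 160 or more, or diastolic of 110 or more.

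In row 1, antihypertensives are optimized first. Cabozantinib then goes down one level when "optimal antihypertensive therapy (usually to include 3 agents) does not result in BP <140 mm Hg systolic or <90 mm Hg diastolic". Symptomatic subjects are interrupted.

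In row 2, the first bullet already calls for a one-level reduction or an interruption, at the investigator's choice. If optimized therapy then "does not result in BP < 140 mm Hg systolic or < 90 mm Hg diastolic, cabozantinib treatment should be dose reduced further"; interruption is the stated alternative. A separate bullet says that cabozantinib "should be dose interrupted if upper limits of systolic BP (≥ 160 mm Hg) are sustained and not adequately manageable". It adds three further grounds: "or if systolic BP is > 180 mm Hg or diastolic BP > 110 mm Hg, or if subject is symptomatic". The last bullet restarts at the most tolerable dose, to "re-escalate only if BP falls to and is sustained at < 140 mm Hg systolic and < 90 mm Hg diastolic".

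Elsewhere, exclusion 3.2.16 defines uncontrolled hypertension as sustained pressure "> 140 mm Hg systolic or > 90 mm Hg diastolic despite optimal antihypertensive treatment". Section 7.2.2 states: "Dose reductions are recommended for events that, if persistent, could become serious or intolerable". It also lists hypertension that stays uncontrolled under best medical management among the reasons to discontinue. Section 7.2.3 has a rule based on CTCAE grade and a discontinuation entry for severe hypertension.

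**The concern.** The two reduction bullets describe failure to reach a target, and the target joins two limits with *or*. Failing to reach one limit *or* the other, taken literally, means reaching neither. A subject who enters row 1 at 158/84 already has a diastolic below 90. On that reading the bullet cannot act for this subject unless diastolic also rises, however long systolic stays at 158.

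Section 7.2.2 lists hypertension among the most frequent cabozantinib events and among those with early onset. It also requires dose decisions to rest on professional readings confirmed by a second measurement. Table 15 holds the only printed mm Hg thresholds for reducing the drug, so its wording is what staff would apply. At stake is whether a subject with one component above target keeps the current dose or goes down a level.

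**Working it through.** No sample size, power or event count is involved; the check is one of logic. Write S for systolic and D for diastolic in mm Hg, after optimized therapy, in an asymptomatic subject.

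**Step 1. The printed trigger.** NOT (S < 140 or D < 90) is the same as S ≥ 140 *and* D ≥ 90. Both targets must be missed.

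**Step 2. The trigger with *and*.** NOT (S < 140 and D < 90) is the same as S ≥ 140 *or* D ≥ 90. Missing either target is enough.

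**Step 3. Comparison with the rest of Table 15.** Entry to each row needs one raised component, which matches step 2 and not step 1. Re-escalation in row 2 requires S < 140 and D < 90. Step 2 is the exact complement of that rule. Under step 1, a subject who misses one target is too hypertensive to re-escalate and yet does not meet the further-reduction trigger.

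**Step 4. Worked readings, row 1.**

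| Reading | Printed bullet acts | With *and* |
|---|---|---|
| 136/84 | no | no |
| 150/96 | yes | yes |
| 158/84 | no | yes |
| 132/106 | no | yes |

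**Step 5. Worked readings, row 2**, after the reduction or interruption that the first bullet requires.

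| Reading | Printed bullet acts | With *and* | Other cover in row 2 |
|---|---|---|---|
| 150/84 | no | yes | none |
| 132/104 | no | yes | none |
| 170/80 | no | yes | still meets row 2 entry (systolic ≥ 160); interruption if sustained and not adequately manageable |
| 132/112 | no | yes | interruption (diastolic > 110) |
| 184/84 | no | yes | interruption (systolic > 180) |

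**Step 6. What remains.** Readings of 160 or more, or 110 or more, still meet row 2 entry or the interruption bullet. The clear gap is S 140-159 with D < 90, or S < 140 with D 90-109.

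**Step 7. Size per subject, from Table 5 in Section 8.** In row 1 at the starting dose, the choice is 40 mg daily kept versus 20 mg daily. In row 2 after a first reduction to 20 mg daily, it is 20 mg daily kept versus 20 mg every other day or interruption. Section 7.2.3 gives another path for a subject withheld at 20 mg: resume at 20 mg if tolerated, otherwise discontinue. The row 2 contrast therefore depends on which section is followed.

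**The case against.** The strongest reply is that no clinician would read the bullets literally. A subject who entered row 1 on systolic alone would not be called controlled because of a diastolic that was never raised, and the entry criteria and re-escalation rule both point to the sensible reading. That is probably right, and it keeps the point minor. It does not justify leaving a printed dose trigger at odds with the table around it.

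A second reply is that other text covers the subject. Section 7.2.2 presents the hypertension table as treatment guidelines, and nothing in the literal reading forbids a reduction. Sections 7.2.2 and 7.2.3 permit reductions generally, and symptomatic subjects are interrupted in both rows. This stands as a limit on the consequences. None of this text gives the mm Hg trigger for a one-level reduction, and discontinuation is a different action. Section 7.2.3 works through CTCAE grades that the documents do not reproduce, so no threshold can be read from it.

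Three stronger readings are tempting.

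- A reader might infer that row 2 subjects with an isolated systolic of 160-180 get no action. The documents do not support this: the first bullet has already required a reduction or interruption, and such readings still meet row 2 entry. The subheading, which refers to subjects not yet on optimized therapy, leaves some room to argue whether entry applies again after optimization. That doubt is too thin to carry the stronger claim.
- A reader might join 3.2.16 to the discontinuation list in 7.2.2 and conclude that a persistent 158/84 must stop the drug, which would contradict Table 15. But 3.2.16 is an eligibility definition, and the protocol does not carry it over to on-treatment decisions. It is useful here only as another example of wording that treats either raised component as uncontrolled.
- A reader might infer a measurable effect on safety rates or progression-free survival. The documents give no figure from which one could be derived.

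**Conclusion.** The wording is wrong as written, and the point is minor. Taken literally, the row 1 reduction bullet and the row 2 further-reduction bullet do not act for an asymptomatic subject who misses only one target. The clear gap is systolic 140-159 or diastolic 90-109, with the other component at target, after optimization. Per subject the difference is one cabozantinib dose level, most plainly 40 mg versus 20 mg daily in row 1. No count or proportion of subjects affected can be given. The conclusion rests on the literal reading of *or*; a site that already reduces when either target is missed would see no change in practice. No endpoint, sample size or analysis is touched.

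**What to change.** Replace *or* with *and* in both bullets. The dose is then reduced by one level (row 1), or reduced further or interrupted (row 2), unless pressure is both below 140 systolic and below 90 diastolic. This uses the form already printed in the table's re-escalation bullet. The cost is one word in each of two bullets, which can go into the next amendment, with no added visits, tests or analyses.

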Serum electrolyte disorders including hyponatremia, hypokalemia, hypomagnesemia, and hypophosphatemia have been reported during treatment with Cabozantinib, and serum electrolyte levels should be monitored frequently while receiving Cabozantinib. Clinically relevant electrolyte disorders should be managed according to the dose modification guidelines as clinically indicated. Standard clinical practice guidelines should be used for management of electrolyte disorders and may include oral or IV replacement.

Endocrine Disorders

Treatment-emergent elevation of thyroid-stimulating hormone (TSH) has been observed with Cabozantinib treatment. Currently available data are insufficient to determine the mechanism of thyroid function test alterations and its clinical relevance. Management of thyroid dysfunction (e.g., symptomatic hypothyroidism) should follow accepted clinical practice guidelines.

Hepatocellular Toxicity

Elevations of aminotransferases (ALT and AST) and bilirubin have been observed during treatment with Cabozantinib. It is recommended that subjects with elevation of ALT, AST, and/or bilirubin have more frequent laboratory monitoring of these parameters. If possible, hepatotoxic concomitant medications should be discontinued in subjects who develop increased values of ALT, AST, or bilirubin, and other causes (e.g., cancer related, infection) should be evaluated.

Management guidelines for hepatotoxicity related to Cabozantinib treatment are in **Appendix E**. More frequent monitoring of transaminases should be considered and study treatment should be held until the etiology of the abnormalities is determined and these abnormalities are corrected or stabilize to clinically acceptable levels (e.g., baseline grade or lower). If hepatic toxicity resolved during a temporary hold and was deemed related to study treatment, then study treatment may be restarted at a reduced dose. Study treatment should be discontinued if hepatic dysfunction is not reversible despite temporary interruption of study treatment.

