7.2.3 Management of Adverse Reactions from Cabozantinib

Withhold CABOZANTINIB for NCI CTCAE Grade 4 adverse reactions, and for Grade 3 or intolerable Grade 2 adverse reactions that cannot be managed with a dose reduction or supportive care.

Upon resolution/improvement (i.e., return to baseline or resolution to Grade 1) of an adverse reaction, reduce the dose as follows:

- If previously receiving 60 mg daily dose, resume treatment at 40 mg daily
- If previously receiving 40 mg daily dose, resume treatment at 20 mg daily
- If previously receiving 20 mg daily dose, resume at 20 mg if tolerated, otherwise, discontinue CABOZANTINIB

Permanently discontinue CABOZANTINIB for any of the following:

- development of unmanageable fistula or GI perforation
- severe hemorrhage
- arterial thromboembolic event (e.g., myocardial infarction, cerebral infarction)
- hypertensive crisis or severe hypertension despite optimal medical management
- nephrotic syndrome
- reversible posterior leukoencephalopathy syndrome

In Patients Concurrently Taking a Strong CYP3A4 Inhibitor: Reduce the daily CABOZANTINIB dose by 20 mg (for example, from 40 mg to 20 mg daily). Resume the dose that was used prior to initiating the CYP3A4 inhibitor 2 to 3 days after discontinuation of the strong inhibitor

In Patients Concurrently Taking a Strong CYP3A4 Inducer: Increase the daily CABOZANTINIB dose by 20 mg (for example, from 40 mg to 60 mg daily or from 20 mg to 40 mg daily) as tolerated. Resume the dose that was used prior to initiating the CYP3A4 inducer 2 to 3 days after discontinuation of the strong inducer. The daily dose of CABOZANTINIB should not exceed 80 mg.

In Patients with Hepatic Impairment: Reduce the starting dose of CABOZANTINIB to 20 mg once daily in patients with mild or moderate hepatic impairment. CABOZANTINIB is not recommended for use in patients with severe hepatic impairment.

Nursing Guidelines

Monitor vital signs prior to infusion, then every 15 minutes until 1 hour after infusion on first dose.

All patients with a history of infusion reactions to this immunotherapy should be monitored every 15 minutes until 1 hour after the end of the infusion.

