Nephrotic syndrome	
 Discontinue Cabozantinib treatment
UC, urothelial carcinoma; UPCR, urine protein/creatinine ratio.	

Table 18. Management of Hepatotoxicity Associated with Cabozantinib

Severity of Transaminase (ALT or AST) and total bilirubin Elevations	Management
If ALT or AST is within normal limits at baseline and increases to $> \text{ULN} - 3.0 \times \text{ULN}$ OR Total bilirubin increases to $> \text{ULN} - 1.5 \times \text{ULN}$	
 Dose adjustment is usually not required. Consider discontinuing concomitant hepatotoxic medications and adding supportive care as indicated.
If elevation of ALT or AST to $> 3.0 - 5.0 \times \text{ULN}$ (total bilirubin $\leq 2.0 \times \text{ULN}$) OR Total bilirubin increases to $> 1.5 - 3.0 \times \text{ULN}$ (ALT or AST $\leq 3.0 \times \text{ULN}$)	
 Interrupt Cabozantinib if lasting longer than 1 week. Restart Cabozantinib after lab abnormalities have resolved to CTCAE Grade ≤ 1 or baseline grade at the same dose level prior to dose interruption or one dose level lower at the discretion of the Sponsor.
If ALT or AST increases to > 5.0 to $\leq 8.0 \times \text{ULN}$, (total bilirubin $\leq 2.0 \times \text{ULN}$) OR Total bilirubin increases to $> 3.0 \times \text{ULN}$ (ALT or AST $\leq 3.0 \times \text{ULN}$)	
 Interrupt Cabozantinib and consider more frequent monitoring of ALT, AST, and bilirubin. Restart Cabozantinib at a reduced dose after lab abnormalities have resolved to CTCAE Grade ≤ 1 or baseline grade. Discontinue if lab abnormalities cannot be reversed despite interruption of Cabozantinib.
ALT or AST $> 8 \times \text{ULN}$ OR ALT or AST $> 3 \times \text{ULN}$ in combination with total bilirubin $> 2 \times \text{ULN}$ without reasonable other explanation, consistent with DILI	
 Discontinue Cabozantinib unless these laboratory abnormalities have recovered to Grade 1 or baseline level after an interruption and the Sponsor has approved reinstitution of Cabozantinib.
ALT, alanine aminotransferase; AST, aspartate aminotransferase; CTCAE, Common Terminology Criteria for Adverse Events; DILI, drug-induced liver injury.	

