Note: The guidance for dose modifications for bilirubin abnormalities applies only to subjects without Gilbert's Disease. Elevations of aminotransferases when hepatic metastases are present may not require dose modifications if there is less than a doubling in the aminotransferases from baseline and if there are no progressive elevations in serum bilirubin concentration or coagulation factors. The following condition requires discontinuation of cabozantinib: Drug-related ALT or AST $> 3 \times \text{ULN}$ in combination with total bilirubin $> 2 \times \text{ULN}$ without other reasonable explanation, consistent with drug-induced liver injury (DILI).	

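### For suspected drug-induced liver injury, the Table 18 row lets cabozantinib resume after recovery and Sponsor approval, while the note under the table requires discontinuation and states no exception

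*Combined protocol and SAP*

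**What the plan says.** Four places in the combined protocol and SAP bear on the point.

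- **Appendix E, Table 18, last row.** The trigger has two limbs: ALT or AST above 8 × ULN, or ALT or AST above 3 × ULN together with total bilirubin above 2 × ULN, "without reasonable other explanation, consistent with DILI". The action is: "Discontinue Cabozantinib unless these laboratory abnormalities have recovered to Grade 1 or baseline level after an interruption and the Sponsor has approved reinstitution of Cabozantinib".
- **Appendix E, note under Table 18.** After a sentence that eases dose modification for some patients with hepatic metastases, the note states: "The following condition requires discontinuation of cabozantinib". The condition that follows is the second limb of the row, with the same thresholds and the same reference to drug-induced liver injury, restricted to drug-related elevations.
- **Section 7.2.2, Hepatocellular Toxicity.** This text refers to Appendix E for management and then adds: "If hepatic toxicity resolved during a temporary hold and was deemed related to study treatment, then study treatment may be restarted at a reduced dose". It calls for discontinuation when the dysfunction does not reverse.
- **Section 7.2.3.** The list headed "Permanently discontinue CABOZANTINIB for any of the following" does not include liver injury.

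**The concern.** The row and the note sit in the same table and describe the same laboratory pattern. One attaches a conditional route back to cabozantinib and the other does not. An investigator whose patient has recovered could follow the row and ask for approval, follow the note and treat the drug as finished, or rely on Section 7.2.2 and restart without asking.

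What is at stake is re-exposure after a serious hepatic event. The protocol itself gives a closely similar pattern special status: Section 10.1 makes ALT or AST at or above 3 × ULN with bilirubin at or above 2 × ULN, and alkaline phosphatase below 2 × ULN, an event of clinical interest. An instruction for an event of that weight should not depend on which line of the table is read.

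**Working it through.** No arithmetic applies, so the texts are compared on trigger, action and route back.

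| Place | Trigger | Action | Route back to cabozantinib |
|---|---|---|---|
| Table 18, last row, limb 1 | ALT/AST > 8 × ULN | Discontinue | Recovery to Grade 1 or baseline after interruption, and Sponsor approval |
| Table 18, last row, limb 2 | ALT/AST > 3 × ULN with bilirubin > 2 × ULN, no other explanation, consistent with DILI | Discontinue | Same as limb 1 |
| Note under Table 18 | As limb 2, and drug-related | Discontinuation required | None stated |
| Section 7.2.2 | Hepatic toxicity in general, related to treatment | Hold | Lower-dose restart after resolution; no Sponsor approval mentioned |

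**Step 1: do the row and the note cover the same patients?** The note uses the thresholds of limb 2 and adds that the elevation is drug-related. Every patient who meets the note's condition therefore also meets the row's.

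**Step 2: does another row of Table 18 take these patients?** No. The two middle rows require either bilirubin at or below 2 × ULN or ALT/AST at or below 3 × ULN. A patient above both limits is outside them, so their restart terms do not apply.

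**Step 3: where do the outcomes part?** Until recovery, the row and the note lead to the same place: cabozantinib is stopped. They part only if the values return to Grade 1 or baseline and restart is considered. With approval, the row then permits resumption. The note, as worded, does not.

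**Step 4: does limb 1 conflict with the note?** No. The note does not mention ALT/AST above 8 × ULN on its own.

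**Step 5: do Sections 7.2.2 and 7.2.3 settle the matter?** No. Section 7.2.2 makes no exception for suspected drug-induced liver injury and omits the approval step, so its wording is more permissive than the row. Section 7.2.3 is silent on liver injury.

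**The case against.** The strongest answer is that the row and the note are compatible. Both begin with discontinuation, and the note does not say that it is permanent. Where the protocol means irrevocable it often says so, as in the QTc text of Section 7.2.2, the list in Section 7.2.3 and Table 19. The note's sentence also has a job that needs no conflict: it follows the easing for hepatic metastases and may simply limit that easing, leaving the row's exception in place. Section 7.2.2, on this view, is general text that defers to the appendix.

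This reading is possible, but the documents do not state it. The note makes no reference to the row. The wording argument is not decisive, because Section 7.2.2 uses plain discontinuation for events such as nephrotic syndrome and reversible posterior leukoencephalopathy syndrome, which Section 7.2.3 lists as permanent. Table 18 also separates interrupting from discontinuing, so a required discontinuation does not naturally read as a temporary hold. The point about Section 7.2.2 stands in part: it does not address drug-induced liver injury by name, so it is better described as an unqualified general allowance than as a third specific rule.

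Three stronger readings may tempt a reader and are not supported:

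- **That Sponsor approval alone reopens treatment under the row.** Recovery after an interruption is also required.
- **That every patient with this pattern is affected.** Those who do not recover, or for whom restart is not considered, stay off cabozantinib under the row and the note alike.
- **That liver metastases, for which Section 3.1.5 sets a separate aminotransferase limit, make the conflict common.** Both the row and the note apply only when there is no other reasonable explanation, so elevations explained by metastases fall outside the disputed condition.

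**Conclusion.** The point holds as an internal inconsistency, mainly within one table, with Section 7.2.2 adding an allowance that matches neither the row nor the note. Followed as written, the texts can produce different re-exposure decisions for the same patient.

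Its reach is narrow: patients who meet the combined aminotransferase and bilirubin criterion, whose values recover, and for whom restart is considered. The documents give no rate for this event, so the number cannot be estimated. With 23 patients planned (Section 9.2), it is probably small.

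The conclusion rests on reading the note as it stands, without an implied reference to the row. If the authors intended the row's exception to apply, the defect is a missing cross-reference, and clarification is still needed. The statistical plan is not affected: Section 9.7.2 keeps patients in the primary analysis whatever happens to their dosing schedule. The reason to act is patient safety and consistent conduct.

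**What to change.** The last row of Table 18, the note beneath it and the hepatocellular text in Section 7.2.2 must be reconciled to one instruction for ALT/AST above 3 × ULN with bilirubin above 2 × ULN consistent with drug-induced liver injury. The choice of instruction belongs to the sponsor and investigators, and this review takes no view on it. Each of the three places should then state that instruction or refer to the place that does.

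If the reconciled text keeps an approval step, it should say whose approval is meant. Section 10.4 describes the Principal Investigator as study sponsor, while Section 8.1 uses the term for the two companies supplying the drugs.

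The cost is a wording amendment. No data collection, sample size or analysis changes.
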